8.1.1.2. PK-PD interactions: myelopoiesis and immunologic response

* While DDIs between imatinib, isoniazid, and rifabutin are no longer a focus of the study, the following language has been left in the protocol as these associations may be analyzed in participants enrolled in the previous protocol in the 50 and 100mg arms. We have also extensively used AI methods these methods to identify drug threshold concentrations associated with adverse events, and drug concentration thresholds associated with good microbial and clinical outcomes (46)· (38, 39, 47)· (48, 49)· (50)· (40). These methods are more accurate than mixed effects modeling, require smaller sample sizes, and are designed to handle both deep and wide data. We will examine the effect imatinib, and the effect of rifabutin and isoniazid PK parameters on imatinib immunological response. We will identify the imatinib concentration threshold associated with optimal hematopoiesis alone and in the presence of the anti-TB drugs rifabutin and isoniazid, using the MARS algorithm in Salford Miner software. Similarly, we will use the same approach to identifier predictors and imatinib concentrations associated with any adverse events.

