8.1 Sample Size Justification and Statistical Analysis

The primary objectives are to determine the effect of imatinib on the numbers of myelomonocytic cells in the blood, assessed as the change between baseline and day 14 of

imatinib only administration. Secondary objectives include analysis of PK measurements, bacterial killing, proteomic evaluations, and immune function evaluations. We will enroll a total of 48 evaluable participants total, 12 across 4 doses of imatinib (50, 100, 200 and 400mg). 12 participants were already enrolled at the 50 mg dose, and 4 at the 100mg dose in the previous version of the protocol.

With 12 participants per dosage arm (N=48), we will have 80% power to reject the null hypothesis of no change versus the alternative hypothesis that imatinib induces an increase in the absolute numbers of myelomonocytic cells per uL of blood that is at least 0.41 of the standard deviation (SD) of the change for the cohort overall and 90% power to detect a 0.48 SD. Our primary analysis will use a linear mixed model that pools data from all time points, thus we anticipate having more power by leveraging the within-person correlation between individuals.

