8.1.1.1. Drug-drug pharmacokinetic interactions

* While DDIs between imatinib, isoniazid, and rifabutin are no longer a focus of the study, the following language has been left in the protocol as these associations may be analyzed in participants enrolled in the previous protocol in the 50 and 100mg arms. We have recently introduced machine learning or artificial intelligence (AI) based algorithms to pharmacometrics to identify PK covariates, including genotypic, demographic, clinical, laboratory features, and concomitant medications (44, 45). We will examine the effect of rifabutin and isoniazid PK parameters, demographic features, laboratory values, and RNA-seq signatures, in each participant, on imatinib PK parameters and variability, and hence identify the DDIs if present. We will compare baseline pre-treatment blood samples with those taken after imatinib alone or after imatinib plus isoniazid and rifabutin. This will be performed using Salford Miner software.

Moreover, algorithms such as MARS give a final output equation of the covariates which can be directly used to identify the optimal dose for use in the case that DDI are identified.

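### Version 5.0 ranks MARS above mixed models without evidence, and plans MARS thresholds and a dose equation with no stated validation, error control or interval

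*Combined protocol and SAP*

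**What the plan says.** All references are to Version 5.0.

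- **Ranking of methods (8.1.1.2).** "These methods are more accurate than mixed effects modeling, require smaller sample sizes, and are designed to handle both deep and wide data". The references nearby are attached to past use of the methods for finding thresholds. No comparison or figure accompanies the sentence.
- **Threshold (8.1.1.2).** "We will identify the imatinib concentration threshold associated with optimal hematopoiesis alone and in the presence of the anti-TB drugs rifabutin and isoniazid", by MARS in a named software package. No settings are given.
- **Dose equation (8.1.1.1).** Algorithms such as MARS "give a final output equation of the covariates which can be directly used to identify the optimal dose for use" if an interaction is identified.
- **Candidate predictors.** For imatinib PK, 8.1.1.1 lists rifabutin and isoniazid PK parameters, "demographic features, laboratory values, and RNA-seq signatures, in each participant". For the immunological response, 8.1.1.2 names imatinib and the PK parameters of the other two drugs. Neither section states how many candidates there are.
- **Adverse events (8.1.1.3).** MARS is applied to an open-ended list of outcomes.
- **Who is analysed.** A note above each section says of the isoniazid and rifabutin interactions that "these associations may be analyzed in participants enrolled in the previous protocol in the 50 and 100mg arms". Section 8.1 gives the numbers: "12 participants were already enrolled at the 50 mg dose, and 4 at the 100mg dose in the previous version of the protocol". The full study is larger: "We will enroll a total of 48 evaluable participants total, 12 across 4 doses of imatinib".
- **Mixed models.** The Study Summary (Statistical Methodology) assigns the relation between imatinib exposure and cell change to mixed models. Section 8.1.1, aim 2, names AUC, peak and trough as the exposure measures.
- **Exploratory label (3.2.2).** It covers only proteomic and transcriptomic changes.

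**The concern.** MARS searches over predictors and over cut-points within each predictor, then keeps what lowers a penalised error. Without calibration, the fact that a knot was kept says little about whether a threshold exists. The plan nevertheless promises to identify a threshold, and says the equation can serve dose identification.

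The ranking sentence makes this worse. The same exposure-response question goes to a mixed model in the Study Summary and to MARS in 8.1.1.2. If they disagree, the only guidance in the text is an unsupported statement that MARS is the more accurate. A chance knot could then be presented as an imatinib threshold in preference to the plan's own model.

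**Working it through.** **Plan's own figure.** There is none to reproduce. No error rate, accuracy or sample-size calculation is given for MARS. By contrast, section 8.1's power figure for the pooled paired change can be checked: 0.41 SD at N = 48 gives 79.4% against the stated 80%.

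**Inputs from the documents.** At most 12 + 4 = 16 people for the isoniazid and rifabutin associations; 48 in total; clearance 14 L/h with 32% variability (1.2.2.1).

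**Assumed, because the plan does not say.** The number of candidates p, the GCV penalty d, knot spacing and the maximum number of terms. Models are additive.

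**Method.** Forward selection of mirrored hinge pairs, then backward pruning by GCV = (RSS/n) / (1 − C/n)², with C = M + d(M − 1)/2 for M terms. Outcome and predictors are independent noise. The result is the share of datasets in which the final model keeps at least one predictor.

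**Noise selection, all knots eligible, up to 15 terms:**

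| Candidates | n = 16, d = 2 | n = 16, d = 3 | n = 48, d = 2 | n = 48, d = 3 |
|---|---|---|---|---|
| 1 | 24% | 11% | 38% | 12% |
| 3 | 53% | 28% | 59% | 27% |
| 5 | 67% | 45% | 70% | 41% |
| 10 | 86% | 63% | 90% | 69% |
| 20 | 94% | 78% | 99% | 88% |

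There were 600 datasets per cell at n = 16 (standard error at most √(0.25/600) = 2 points) and 150 at n = 48 (at most 4 points).

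**Sensitivity at n = 16.**
- At most 7 terms, with AUC = dose/CL as one candidate (d = 2/3): 24%/12% with 1 candidate, 51%/28% with 3, 92%/70% with 10.
- Limits of 5, 10 and 21 terms (d = 3): 10-14% with 1 candidate and 77-80% with 20, so the term limit matters little.
- Spaced knots (d = 3): 5% with 1 candidate and 38% with 10.
- Over all settings tried with 1 to 20 candidates: about 0% (d = 4, charged on every basis function) to 94% (d = 2, all knots).

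**Benchmark.** Unadjusted tests at 0.05 on 10 independent candidates give 1 − 0.95¹⁰ = 40% with any false positive. MARS at d = 3 with all knots gives 63%.

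**Reading the table.** AUC, peak and trough of imatinib make 3 candidates. They are correlated, so their rate should lie between the rows for 1 and 3. If the same three measures were used for all three drugs, that would be 3 × 3 = 9 candidates, near the row for 10 but again reduced by correlation.

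**Precision of a real threshold.** Predictor uniform on 0 to 1, true knot at 0.5, R² = 0.30, knot chosen by least squares, 1,500 datasets:

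| n | 5th to 95th percentile of knot | Middle half |
|---|---|---|
| 16 | 0.08 to 0.92 | 0.26 to 0.73 |
| 48 | 0.06 to 0.95 | 0.35 to 0.66 |

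At n = 16 the estimate covers nearly the whole range. At 48 the middle half narrows from 0.47 to 0.31, but the tails do not. An interval is needed at either size.

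**The case against.** The strongest defence is that little depends on these analyses. The isoniazid and rifabutin interactions are no longer a focus and are optional. The dose sentence describes what such algorithms can do if an interaction is found; it does not schedule a dose decision. The Introduction requires exposure-efficacy and exposure-safety data to be considered with the DSMB and DAIDS before recommendations for later studies. The primary analysis is a mixed model, and the exposure-response mixed model and the three exposure measures are already planned. The group's cited earlier work may include validation that cannot be seen here. All of this stands. It limits the harm, but it leaves the ranking sentence unsupported and the MARS output uncalibrated.

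Three stronger readings are tempting and fail:

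- *MARS overfits here because there are only 16 people.* The rates at 48 are no lower overall. Candidate count, penalty and knot rules drive them.
- *The simulation disproves the accuracy claim.* It contains no mixed-model comparator. It shows only that a retained knot cannot be relied on without calibration.
- *The plan derives its threshold and a dose from 16 people and a long predictor list.* The 16-person limit clearly covers only the isoniazid and rifabutin associations. The participants for the imatinib-alone threshold are not stated and could number 48. The list with laboratory values and RNA signatures belongs to the PK covariate analysis, not to the threshold.

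**Conclusion.** The point holds in this form. Version 5.0 makes an unsupported superiority claim for its machine-learning methods, plans MARS thresholds and a dose-usable equation with no stated calibration or interval, and does not say whether MARS or the mixed model governs the exposure-response conclusion. With all knots eligible and a GCV penalty of 2 to 3, a predictor is kept from pure noise in roughly 10-25% of 16-person datasets with 1 candidate and 60-90% with 10. Those figures rest on settings the plan does not give; the range of about 0% to 94% across other settings is itself a reason to specify and calibrate. The isoniazid and rifabutin output rests on at most 16 people, and fewer if some left the PK studies after stopping drug. The primary endpoint is not affected. This should be corrected in the analysis plan.

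**What to change.** 1. Delete the accuracy and sample-size sentence in 8.1.1.2.
2. State that the exposure-response conclusion comes from the mixed model named in the Study Summary.
3. Label all MARS output exploratory, and output from the 16 earlier participants descriptive.
4. For the imatinib-alone threshold, use day-14 data from all evaluable participants, with AUC, peak and trough as the fixed predictors. State the MARS settings in advance.
5. Report every fitted threshold with a permutation p-value (cell changes permuted across participants and the whole search rerun each time) and a bootstrap 95% interval for the knot. Call it a finding only if p < 0.05. Permutation holds the false-finding rate for that search at about 5% whatever settings are chosen, and reporting every threshold avoids selective reporting.
6. Remove the statement in 8.1.1.1 that the equation can be used directly to identify a dose.

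The cost is a few sentences and a little computing. The downside is that fewer thresholds will be claimed.

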8.1.1.3. PK-PD interactions: adverse events

* While DDIs between imatinib, isoniazid, and rifabutin are no longer a focus of the study, the following language has been left in the protocol as these associations may be analyzed in participants enrolled in the previous protocol in the 50 and 100mg arms. The AI algorithm MARS will be used to identify predictors of imatinib, rifabutin, and isoniazid concentrations associated with any of these adverse events, following our methods in Modongo et al (50). Outcomes examined in relation to imatinib, isoniazid, or rifabutin concentrations will be any participant-reported adverse events, including diarrhea, ECG changes, changes in liver function tests, neutropenia, thrombocytopenia, anemia, changes in other serum chemistries, as well as other symptoms and signs.

8.1.2 Interim Analysis

Given imatinib is an FDA-approved drug with a known safety profile, we expect the doses used in this study to be well tolerated. After the first 6 participants in the 200mg dose group have completed the day 28 follow-up visit, the study team, the Data Safety Monitoring Board (DSMB),

the Independent Safety Monitor, and the Sponsor will evaluate the safety data and determine via email whether it is safe to proceed to enrolling in the 400mg dose group after the previous group is fully enrolled. Note that since 42-day follow-up is required for a participant that “counts” toward the 6 needed for follow-up safety analysis, if any of the first 6 participants in a dose group do not complete the study to day 42, we will need to include other participants who complete the day 42 visit in order to fulfill the requirement.

8.1.3 Safety Analysis

All participants entered into the study who take at least one dose of imatinib will have detailed information collected on AEs for the overall study safety analysis. An Independent Safety Monitor (ISM) will review individual and summary reports of AEs in real time as they occur, as well as scheduled formal review of AEs and clinical laboratory results on a weekly basis during the study. SAEs will be reported to the Investigator within 24 hours of awareness of occurrence and the Investigator will then assess the events and report them to the Sponsor (DAIDS), the FDA and to the Emory IRB as described in [Section 9.4](#). All SAEs will be reported to DAIDS in an expedited fashion, within 3 days of occurrence, in accordance with DAIDS requirements.

8.2 Participant Population(s) for Analysis

All-treated population: Any participants enrolled into the study who receive at least one dose of investigational product will be analyzed for myelopoiesis, safety, and other immune parameters.

Protocol-compliant population: Effects of imatinib on myelopoiesis and other immunologic parameters will also be assessed specifically in those with acceptable protocol-compliance for evaluable data – participants who have taken $\geq 85\%$ of all doses of study drug and completed visits to day 14.

9 Safety and Adverse Events

9.1 Definitions

9.1.1 Adverse Event

An **adverse event** is any untoward medical occurrence associated with the use of a drug in humans whether or not considered drug related.

9.1.2 Serious Adverse Event

Serious Adverse Event

Adverse events are classified as serious or non-serious. A **serious adverse event** is any AE that:

- Is fatal
- Is life-threatening
- Requires or prolongs an inpatient hospital stay
- Results in persistent or significant disability or incapacity
- Is a congenital anomaly or birth defect
- Is an important medical event

Important medical events are those that may not be immediately life threatening, but are clearly of major clinical significance. They may jeopardize the participant, and may require intervention to prevent one of the other serious outcomes noted above. For example, drug overdose or abuse, a seizure that did not result in in-patient hospitalization, or intensive treatment of bronchospasm in an emergency department would typically be considered serious.

All adverse events that do not meet any of the criteria for serious should be regarded as **non-serious adverse events**.

9.2 Recording and Grading of Adverse Events

At each contact with the participant during the study period, which includes every visit up to day 42, the investigator will seek information on adverse events by specific questioning and, as appropriate, by examination. Information on all adverse events will be recorded immediately in the source document, and also in the appropriate adverse event module of the case report form (CRF). All clearly related signs, symptoms, and abnormal diagnostic procedures results will be recorded in the source document, and grouped under one diagnosis.

AEs will be graded using the FDA Guidance Document, "Toxicity Grading Scale for Healthy Adult and Adolescent Volunteers Enrolled in Preventive Vaccine Clinical Trials Guidance for Industry," September 2007, except when the specific AEs are not represented in this document. In these cases, we will also use the DAIDS table for Grading the Severity of Adult and Pediatric Adverse Events, Corrected Version 2.1, July 2017, or the Common Terminology Criteria for Adverse Events (CTCAE) Version 5.0, November 2017, as applicable. The clinical course of each event will be followed until resolution, stabilization, or until it has been determined that the

study intervention or participation is not the cause. Serious adverse events that are still ongoing at the end of the study period will be followed up to determine the final outcome. Any serious adverse event which we become aware of through a passive basis (participant reporting back to the study team, or through publicly available information), which occurs after the study period (after day 42) and is considered to be possibly related to the study intervention (suspected, unexpected serious adverse reactions, or SUSARs) or study participation will be recorded and reported immediately.

Note: Page 9 of the 2007 FDA Guidance Document describes two methods of AE grading for low hemoglobin. The first method is based on lab value ranges. The second is based on decreased readings compared to the subject's baseline reading, with Grade 1 AE assigned for "Any decrease – 1.5" gm/dL change from baseline value. For purposes of this study, hemoglobin readings in this category will not be recorded as Grade 1 AEs. All other criteria for low hemoglobin AE, as described in the FDA document, remain in effect. If a hemoglobin reading is classified as AE using both methods of grading, only one AE will be reported (as the higher grade if different grades are obtained using the two methods).

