9.2 Recording and Grading of Adverse Events

At each contact with the participant during the study period, which includes every visit up to day 42, the investigator will seek information on adverse events by specific questioning and, as appropriate, by examination. Information on all adverse events will be recorded immediately in the source document, and also in the appropriate adverse event module of the case report form (CRF). All clearly related signs, symptoms, and abnormal diagnostic procedures results will be recorded in the source document, and grouped under one diagnosis.

AEs will be graded using the FDA Guidance Document, "Toxicity Grading Scale for Healthy Adult and Adolescent Volunteers Enrolled in Preventive Vaccine Clinical Trials Guidance for Industry," September 2007, except when the specific AEs are not represented in this document. In these cases, we will also use the DAIDS table for Grading the Severity of Adult and Pediatric Adverse Events, Corrected Version 2.1, July 2017, or the Common Terminology Criteria for Adverse Events (CTCAE) Version 5.0, November 2017, as applicable. The clinical course of each event will be followed until resolution, stabilization, or until it has been determined that the study intervention or participation is not the cause. Serious adverse events that are still ongoing at the end of the study period will be followed up to determine the final outcome. Any serious adverse event which we become aware of through a passive basis (participant reporting back to the study team, or through publicly available information), which occurs after the study period (after day 42) and is considered to be possibly related to the study intervention (suspected, unexpected serious adverse reactions, or SUSARs) or study participation will be recorded and reported immediately.

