The primary outcome is the change in the numbers of myelomonocytic cells in the blood between baseline and day 14 of the study. The change in these cells will be estimated with mixed models, combining all dose groups, with interactions between dose and each time point. Secondary efficacy analyses will also use mixed models to determine the relationship between imatinib exposures and change in the numbers of myelomonocytic cells at each dose separately and in the pooled dose strata. Similar analyses will be used to assess bacillary killing, as determined by the Whole Blood Bactericidal Assay (WBA), using bacille Calmette-Guerin (BCG), at day 14.

Safety

The incidence of all adverse events and in particular grade 3 or 4 adverse events and SAEs during all follow-up time will be determined using point estimates and 95% CIs.

Pharmacokinetic analysis

Pharmacokinetic (PK) parameters, including absorption, distribution, and metabolism, will be determined using S-ADAPT software utilizing a compartmental PK analysis approach and summarized by treatment regimen.

Study design

Dose-escalation trial with PK components

Power and Sample Size Analysis

At completion of the study, 48 participants with evaluable data will provide 90% power to detect a 0.48 SD in the change in the number of myelomonocytic cells on imatinib. Within each dose stratum, we will have 90% power to detect a 1.03 SD change.

Safety Evaluations

Clinical and laboratory adverse events including ECG changes will be monitored prospectively while on study drug and at 14 days after completion of imatinib.

Study Progress and Safety Monitoring Plan

The Independent Safety Monitor, PI and study team, Data Safety Monitoring Board (DSMB), and Sponsor will be responsible for monitoring the data quality and the ongoing safety of participants. Twelve participants will be enrolled into each dosage arm in an ascending manner, starting with the 100 mg imatinib dose. A safety analysis will be performed by the team and the DSMB after complete safety data are available from 6 participants within a stratum. If safe, and after a total of 12 participants are enrolled for the first stratum, then the next higher dose will begin enrolling participants. Enrollment will proceed in this manner until the sample size has been reached. Formal safety analysis will then occur using the data from all dose groups.

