3.1 General Design

This is an open label trial evaluating the safety, PK and immunologic effects (PD) of different doses of imatinib in healthy adult volunteers. In this revised protocol, 32 participants will be enrolled in a dose-escalating fashion to receive one of three imatinib doses alone for 28 days. Because 4 participants received imatinib at 100mg in a previous protocol, 8 participants will receive 100mg daily under this revised protocol, to complete dosing of 12 participants at 100mg imatinib daily. Safety evaluation to day 42 follow-up will be conducted for the first 6 participants in the 100mg stratum (4 previous participants, plus 2 more enrolled through this amended protocol) while the remaining 6 participants are continuing to accrue to the study. Once the safety evaluation for the first 6 participants is finalized, and enrollment of a total of 12 participants in the 100mg stratum is complete, we will begin enrolling 12 participants in the next

dose stratum (200 mg/daily). Enrollment will proceed in this fashion, with safety evaluation after the first 6 participants at each dose. In this manner, 12 participants will be allocated to each imatinib dose, proceeding from 100mg to 200mg and finally from 200mg to 400mg daily.

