Similarly, let $t_{14_{ij}}$ = day14 indicator and $dose_{k_{ij}}$ = dose k indicator for individual i , time j , where $k=2,3,4$. Let r_i be the random intercept term for person i and let error_{ij} be the mean 0 independent error term for person i at time j .

$$Y_{ij} = b_0 + b_1 t_{14_{ij}} + b_2 t_{14_{ij}} * dose_{2_{ij}} + b_3 t_{14_{ij}} * dose_{3_{ij}} + b_4 t_{14_{ij}} * dose_{4_{ij}} + r_i + \text{error}_{ij}$$

b_0 = baseline myelopoiesis

b_1 = day14 change from baseline for dose 1

b_2 = difference between dose 2 and dose1 day14 change from baseline

b_3 = difference between dose 3 and dose1 day14 change from baseline

b_4 = difference between dose 4 and dose1 day14 change from baseline

$(4b_1+b_2+b_3+b_4)/4$ is the average Day 14 change from baseline pooled across the 4 doses in, i.e. the primary endpoint

$b_2 - b_3$ is the between dose difference in the day14 change from baseline for dose 2 and 3; similar comparisons can be for each distinct pair of doses for day14 change from baseline.

AE analysis

We will estimate proportion of clinical and laboratory adverse events, along with 95% exact Clopper-Pearson CI. AE rates will be summarized separately by dose and then overall. All participants who take at least 1 dose will be included in assessments of safety.

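### The grade 1 hemoglobin rule differs between Version 3.0 and Version 5.0 and no re-grading is planned, so all-grade AE rates by dose may be inflated at 50 mg and partly at 100 mg

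*Combined protocol and SAP*

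**What the plan says.** **Grading rule.** Version 5.0, section 9.2, notes that the FDA 2007 scale grades low hemoglobin in two ways: by laboratory range and by fall from the participant's baseline. It then removes the lowest step of the second method, any fall up to 1.5 g/dL: "For purposes of this study, hemoglobin readings in this category will not be recorded as Grade 1 AEs". The exemption goes no further: "All other criteria for low hemoglobin AE, as described in the FDA document, remain in effect". Section 9.2 of Version 3.0 (with its three letters of amendment) names the same scale, "AEs will be graded using the FDA Guidance Document", and contains no hemoglobin note. Both versions require AEs to be entered in the source document and CRF as they are found.

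**Who came from where.** Version 5.0, section 8.1, counts earlier participants in the 48: "12 participants were already enrolled at the 50 mg dose, and 4 at the 100mg dose". Section 3.1 completes the second stratum: "8 participants will receive 100mg daily under this revised protocol".

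**Planned output.** The Study Summary of Version 5.0 reports "The incidence of all adverse events and in particular grade 3 or 4 adverse events", together with SAEs, as point estimates with 95% CIs. The AE analysis in 8.1 estimates proportions of clinical and laboratory AEs with exact Clopper-Pearson intervals, and "AE rates will be summarized separately by dose and then overall". Neither place sets a minimum grade, separates protocol versions or describes re-grading.

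**The concern.** An AE proportion compared across doses needs one definition of an AE at every dose. Here the definition appears to change with protocol version, and version is almost fully confounded with dose: the older rule at 50 mg, a mixture at 100 mg, and the newer rule at 200 and 400 mg.

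The older rule is the more inclusive one. If the 16 stay as recorded, their count of hemoglobin AEs can only be equal to or higher than it would be under the newer rule. Any distortion therefore raises the lowest dose relative to the highest. It could mask a real dose-related rise in mild laboratory toxicity, or make 50 mg look less well tolerated than it was. The safety of different doses is a primary objective and the study drug is being examined for hematologic effects, so this part of the AE table will be read closely.

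**Working it through.** **1. Counts.** Carried over: 12 + 4 = 16. New under Version 5.0: 8 + 12 + 12 = 32. Total: 16 + 32 = 48, which reproduces the plan's figure. The share of each stratum from the earlier version is:

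| Dose | From earlier version | Share s |
|---|---|---|
| 50 mg | 12 of 12 | 1 |
| 100 mg | 4 of 12 | 1/3 |
| 200 mg | 0 of 12 | 0 |
| 400 mg | 0 of 12 | 0 |
| Overall | 16 of 48 | 1/3 |

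**2. Artefact in the hemoglobin AE proportion.** Let q be the probability that a participant is counted only because of the dropped category: the largest fall from baseline is above 0 and at most 1.5 g/dL, and no value meets the laboratory-range method. If AEs are tabulated as recorded, the expected artefact is q × s. The documents give no value for q, so it is assumed:

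| q (assumed) | 50 mg | 100 mg | 200 and 400 mg | Overall |
|---|---|---|---|---|
| 0.10 | 10% | 3% | 0 | 3% |
| 0.25 | 25% | 8% | 0 | 8% |
| 0.50 | 50% | 17% | 0 | 17% |
| 0.83 | 83% | 28% | 0 | 28% |

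**3. Where 0.83 comes from, and how far to trust it.** Table 1 of both versions schedules a baseline count and five later ones (days 7, 14, 21, 28 and 42). With no drug effect and six exchangeable readings, baseline is the lowest with probability 1/6, so the chance of at least one fall is 1 − 1/6 = 5/6 = 83%. This still has to be split at 1.5 g/dL. A simulation (400,000 draws, normal readings, unrounded) gives the share whose largest fall is at most 1.5 g/dL:

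| Assumed mean fall after baseline | Within-person SD 0.3 | SD 0.5 | SD 0.7 |
|---|---|---|---|
| 0 | 83% | 77% | 63% |
| 0.3 g/dL | 95% | 78% | 59% |
| 1.0 g/dL | 67% | 45% | 34% |
| 1.5 g/dL | 17% | 17% | 16% |

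The SDs and mean falls are assumptions. Under each assumption the entry is a ceiling for q, because participants who also meet the laboratory-range method must be taken out and every small fall must have been recorded. With a large true fall, more participants pass 1.5 g/dL and are AEs under both rules, so q drops.

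**4. Artefact in the any-AE proportion.** A participant with another AE is already counted. If the true any-AE rate is p at every dose and hemoglobin AEs are independent of the others, the tabulated rate is p + (1 − p) × q × s. With p = 0.50 assumed:

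| q | 50 mg | 100 mg | 200 and 400 mg |
|---|---|---|---|
| 0.10 | 55% | 52% | 50% |
| 0.50 | 75% | 58% | 50% |
| 0.83 | 92% | 64% | 50% |

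**5. Under one rule.** If all 48 are graded under the same rule, the difference in definition is zero at every dose, whatever q is.

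**The case against.** The strongest reply is that the rule actually applied to the 16 cannot be seen. Version 5.0 places them in a previous or last version without naming it. Its history lists a Version 4.0, dated September 13, 2021, whose text is not supplied. Their regimen, imatinib followed by imatinib with rifabutin and isoniazid, matches Version 3.0, but grading under that text is an inference. Version 3.0 also does not say how the scale's two hemoglobin methods were to be used. The Version 5.0 note is worded for the study as a whole and could be read as a clarification that covers everyone. All of this stands, and it makes the point conditional. It does not remove it: the note speaks of what will be recorded from then on, AEs in the 16 should already be in the database, and nothing says that they are to be changed.

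A reader might infer that the table will show 10 of 12 hemoglobin AEs at 50 mg against 0 of 12 at the top doses, and that so sharp a contrast is statistically decisive. The documents do not support this. Those counts come from an assumed model with no drug effect. Laboratory-range AEs and falls above 1.5 g/dL are still recorded at 200 and 400 mg. The only hemoglobin indication in the documents (section 12.1 of both versions) is that most CML patients fall by 1 to 2 units (printed as mg/dL). If that were g/dL and applied to these volunteers, q would be well below 0.83. The plan also specifies interval estimates and no between-dose test of AE rates.

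It is also fair to say that re-grading will not make 50 mg fully comparable. The 16 were assigned rifabutin and isoniazid from day 15, and scheduled blood draws total 295 mL in Version 3.0 against 213 mL in Version 5.0. These are separate limits, and removing one known difference in definition is still worthwhile.

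**Conclusion.** The point holds in conditional form. As written, the plan appears to combine two definitions of a grade 1 hemoglobin AE along the dose axis. If AEs are tabulated as recorded, the all-grade and laboratory AE proportions may be inflated at 50 mg, by one third as much at 100 mg and overall, and not at 200 or 400 mg. The direction follows from the two rules. The size cannot be read from the documents: the illustrations run from 10% and 3% (q = 0.10) to 83% and 28% (q = 0.83) for hemoglobin AEs at 50 and 100 mg, and are smaller for any AE.

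This rests on three assumptions: the 16 were graded under the supplied Version 3.0 text, small falls were in fact recorded as AEs, and those records enter the tables unchanged.

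Two wider readings are not supported. Version 5.0 does not exempt every fall up to 1.5 g/dL, because a value that meets the laboratory-range method is still an AE. The main safety conclusion is not at risk from this rule either: the primary safety endpoint is related grade 3 or 4 AEs and SAEs, and the escalation and halting criteria based on grade 3 or higher events and SAEs do not depend on a grade 1 category. What is affected is a planned descriptive output that bears on the safety objective.

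**What to change.** Add to the AE analysis in section 8.1 of Version 5.0:

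*For AE summaries, hemoglobin AEs will be re-derived for all participants from recorded hemoglobin values under the single rule in Version 5.0 section 9.2 (both FDA methods, excluding the grade 1 category of any decrease to 1.5 g/dL from baseline). AEs as originally recorded under earlier versions will be listed separately.*

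The cost is one sentence and a short derivation program. Hemoglobin was scheduled at the same study days in both versions, so no new data are needed. The change concerns tabulation only: no dose, visit or clinical action changes, and the original records are kept. If the grades have already been brought onto one rule, the sentence simply documents it. A footnote to the AE tables should still say that the 16 earlier participants were assigned rifabutin and isoniazid in the second dosing interval.
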